7.4. End of Study

The end of study is the last subject, last assessment collection for final collection of data for the primary outcome.

8. STUDY POPULATION

8.1. Inclusion Criteria

To be eligible to participate in this study, candidates must meet the following eligibility criteria at the Screening Visit:

- 1. Ability to understand the purpose and risks of the study and provide signed and dated informed consent and authorization to use protected health information (PHI) in accordance with national and local subject privacy regulations.
- 2. Age ≥ 18 years at the time of informed consent.
- 3. Reside in the US and have a confirmed diagnosis of a relapsing form of MS and satisfy the therapeutic indication as described in the local label.
- 4. Female subjects of childbearing potential who are not surgically sterile must practice effective contraception during their participation in the study and be willing and able to continue contraception for 30 days after they complete or withdraw from the study. All men must practice effective contraception and should not donate sperm, throughout the study and for at least 90 days after their last dose of study treatment.
- 5. As perceived by the Investigator, have the ability to comply with all requirements of the study protocol and to operate the eDiary required to record GI-related events.

8.2. Exclusion Criteria

Candidates will be excluded from study entry if any of the following exclusion criteria exist at the Screening Visit or at the timepoint defined in the individual criterion listed:

- 1. Inability to comply with the study requirements or, at the discretion of the Investigator, is deemed unsuitable for study participation.
- 2. Female subjects who are currently pregnant or breastfeeding or who are considering becoming pregnant during the study.
- 3. History of significant GI disease (e.g., irritable bowel disease, peptic ulcer disease, history of major GI surgery, eosinophilic GI disease, or food allergies).
- Chronic use (≥7 consecutive days) of bismuth subsalicylate, simethicone, calcium carbonate, loperamide, proton-pump inhibitors, or ondansetron within 1 month prior to the Screening Visit. From Screening up to Day 10, use of such therapies is not permitted. From Day 11 (inclusive), subjects are permitted to take these therapies.
- 5. Use of the following medications: montelukast, immunotherapy, mast cell stabilizers, or parenteral, inhaled, or oral steroids up to 1 month prior to the Screening Visit. Use of these medications is also not permitted for the duration of the study (except for the use of montelukast as per study protocol) and will lead to discontinuation.
- 6. Treatment with montelukast is contraindicated for any reason.

CONFIDENTIAL

- 7. Exposure to fumarates in the 3 months prior to the Screening Visit. Exposure is also not permitted for the duration of the Screening Period.
- 8. Have 1 or more major comorbidities that, in the opinion of the Investigator, may affect the outcome of the study.
- 9. History of malignancy (except for basal cell carcinoma that had been completely excised prior to study entry), severe allergic or anaphylactic reactions or known drug hypersensitivity, abnormal laboratory results indicative of any significant disease, and/or a major disease that would preclude participation in a clinical study.
- 10. Prior confirmed diagnosis or medical history of chronic eosinophilia.
- 11. Current enrollment in any other interventional clinical studies.
- 12. Subjects meeting the inclusion criteria as defined in Section 8.1, and who do not meet any of the exclusion criteria will be eligible to commence with a 2-week Screening Period. At the end of the Screening Period (at the Randomization Visit), GSRS scores and concomitant medication will be evaluated. Subjects who meet the following criterion will be excluded from further study participation: a GSRS score of ≥5 in 1 question for 1 day, a GSRS score of ≥4 in 1 question for 2 consecutive days, or a GSRS score of ≥3 in 1 question for 3 consecutive days.
- 13. Subjects who did not meet the required eDiary compliance (≥75%) in the 14 days prior to randomization.

9. ENROLLMENT AND RANDOMIZATION PROCEDURES

Once the investigational site has been activated for study participation, subjects may be enrolled if they have met the inclusion criteria in Section 8.1 and have not been excluded based on the exclusion criteria in Section 1.

9.1. Enrollment and Screening

Subjects must be consented before any screening tests or assessments are performed. At the time of consent, the subject will be considered enrolled into the study. Participating study sites are required to document all screened candidates initially considered for inclusion in this study. If a subject is excluded from the study, the reasons for exclusion will be documented in the subject's source documents and on the screening log. Subjects will be screened and eligibility will be confirmed after all screening assessments (Screening Visit and 2-week [+14 days] Screening Period) have been completed and after the Investigator has verified that they are eligible per the criteria in Sections 8.1 and 1.

9.2. Randomization of Subjects

Subjects must be consented before any screening baseline tests or assessments are performed. At the time of consent, the subject will be registered into the study. Participating study sites are required to document all registered candidates initially considered for randomization in the study. If the subject is not randomized in the study, the reasons will be documented in the subject's source documents and on the registration log.

Subjects will be randomized at the Randomization Visit. At this visit, eligible subjects will be randomized to 1 of 2 treatment arms (DMF + montelukast or DMF + placebo) in a 1:1 ratio. Subjects will be instructed not to take the blinded randomized study treatment until they receive an alert through their eDiary. This alert will appear if a subject meets the criteria of GSRS score of ≥ 3 in 1 question for 1 day or a GSRS score of ≥ 2 in 1 question for 2 consecutive days.

No subjects may begin treatment prior to randomization and assignment of a unique subject identification number. Any subject identification numbers that are assigned will not be reused, even if the subject does not receive treatment. Subject identification numbers will be assigned by the Interactive Voice and Web Response System (IXRS).

Refer to the Study Reference Manual for details on registration.

As confirmation, Biogen will provide the Investigator with verification of the subject's registration.

9.3. Blinding Procedures

All study staff will be blinded to the subject treatment assignments. To maintain the study blind, it is imperative that subject treatment assignments are not shared with the subjects, their families, or any member of the study team, either at the study site or at Biogen, except the unblinded Pharmacist (or designee) and the unblinded Pharmacy Monitor.

CONFIDENTIAL

10. TREATMENT OF SUBJECTS

Refer to Section 11 (Study Treatment Management) for specifics on the preparation, storage, handling, disposal, and accountability of study treatment.

10.1. Study Treatment Schedule and Administration

Refer to Section 4.1 for a schematic on the study design.

10.1.1. Dimethyl Fumarate

Subjects will receive a supply of commercial DMF through their specialty pharmacy or, in the case of insufficient insurance coverage, through the Biogen Patient Services Free Drug Program.

Dimethyl fumarate should be administered according to the prevailing product label (i.e., USPI). Dimethyl fumarate will be administered orally as 120 mg twice daily during the first 7 days and as 240 mg twice daily thereafter.

Subjects should swallow each DMF capsule whole. The capsule and its contents are not to be crushed, divided, dissolved, sucked, or chewed.

Subjects are to contact the Investigator immediately if more than the prescribed dose is taken.

If a dose is missed, the missed dose can be taken if there is at least 4 hours between the morning and evening doses. Otherwise, treatment should be continued with the next dose as planned.

After Day 10, dose modifications are at the discretion of the Investigator. The prevailing product label (i.e., USPI) should be used as a guideline. Dose modifications should be captured in the case report form (CRF).

10.1.1.1. Treatment Precautions

Refer to the Package Insert for the treatment precautions.

10.1.1.2. Treatment Adherence

Compliance with dosing will be monitored and recorded by study site staff. Subjects are to return all unused DMF and used and unused packaging at each visit. Study site staff will be responsible for recording study treatment accountability and treatment compliance information based on the unused study treatment returned by the subject at each visit.

10.1.2. Montelukast and Placebo

10.1.2.1. Administration

Montelukast (10 mg once daily in the evening) should be administered according to the prevailing product label (Singulair[®]). Randomized treatments (montelukast or placebo) will be administered only until Week 8 of the study.

CONFIDENTIAL

If a subject does not remember to take a dose within 8 hours of the scheduled time (i.e., at least 4 hours before the next scheduled dose), the dose should be skipped, and the next dose should be taken as scheduled. Doses should not be doubled-up, or a missed dose taken the next day, to make up for missed doses.

10.1.2.2. Treatment Precautions

Refer to the Package Insert for treatment precautions [SINGULAIR® USPI 2014].

10.1.2.3. Treatment Adherence

Compliance with dosing will be monitored and recorded by study site staff. Subjects are to return all unused study treatment and used and unused packaging at each visit. Study site staff will be responsible for recording study treatment accountability and treatment compliance information based on the unused study treatment returned by the subject at each visit.

10.2. Continuation of Treatment

Dimethyl fumarate and montelukast are approved treatments in the US, and continuing treatment following completion of the study requirements will be left to the discretion of the subject and Investigator.

10.3. Concomitant Therapy and Procedures

A concomitant therapy is any drug or substance administered between the time the subject is enrolled in the study and the Safety Follow-Up Telephone Interview/ET Visit.

Apart from the treatments listed below and those listed in the exclusion criteria (see Section 1), the use of concomitant medications is left to the discretion of the Investigator. The prevailing product label should be used as a guideline.

A concomitant procedure is any therapeutic intervention (e.g., surgery/biopsy and physical therapy) or diagnostic assessment (e.g., blood gas measurement and bacterial cultures) performed between the time the subject is enrolled in the study and the Safety Follow-Up Telephone Interview/ET Visit.

10.3.1. Prohibited Concomitant Medications

Use of symptomatic treatments to treat GI symptoms is prohibited, with the exception of therapies described below.

10.3.2. Symptomatic Therapy to Treat Dimethyl Fumarate-Related Gastrointestinal Events

From Day 10 onward, but not before, subjects may use the following medications: bismuth subsalicylate, simethicone, calcium carbonate, loperamide, proton-pump inhibitors, and ondansetron.

CONFIDENTIAL

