	4.	Female subjects of childbearing potential who are not surgically sterile must practice effective contraception during their participation in the study and be willing and able to continue contraception for 30 days after they complete or withdraw from the study. All men must practice effective contraception and should not donate sperm, throughout the study and for at least 90 days after their last dose of study treatment.			
	5.	As perceived by the Investigator, have the ability to comply with all requirements of the study protocol and to operate the eDiary required to record GI-related events.			
	Candidates will be excluded from study entry if any of the following exclusion criteria exist at the Screening Visit or at the timepoint defined in the individual criterion:				
	1.	Inability to comply with the study requirements or, at the discretion of the Investigator, is deemed unsuitable for study participation.			
	6.	Female subjects who are currently pregnant or breastfeeding or who are considering becoming pregnant during the study.			
	7.	History of significant GI disease (e.g., irritable bowel disease, peptic ulcer disease, history of major GI surgery, eosinophilic GI disease, or food allergies).			

8. Chronic use (\geq 7 consecutive days) of bismuth

CONFIDENTIAL

subsalicylate, simethicone, calcium carbonate, loperamide, proton-pump inhibitors, or ondansetron within 1 month prior to the Screening Visit. From Screening up to Day 10, use of such therapies is not permitted. From Day 11 (inclusive), subjects are permitted to take these therapies.

- 9. Use of the following medications: montelukast, immunotherapy, mast cell stabilizers, or parenteral, inhaled, or oral steroids up to 1 month prior to the Screening Visit. Use of these medications is also not permitted for the duration of the study (except for the use of montelukast as per study protocol) and will lead to discontinuation.
- 10. Treatment with montelukast is contraindicated for any reason.
- 11. Exposure to fumarates in the 3 months prior to the Screening Visit. Exposure is also not permitted for the duration of the Screening Period.
- 12. Have 1 or more major comorbidities that, in the opinion of the Investigator, may affect the outcome of the study.

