4. STUDY SCHEMATIC AND SCHEDULE OF EVENTS FOR STUDY 109MS414

4.1. Study Schematic

Figure 1: Study Design

Abbreviations: BID = twice daily; DMF = dimethyl fumarate; GI = gastrointestinal; QD = once daily. *Use of symptomatic therapies, as specified in Section 10.3.2, is permitted from Day 10 onward.

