6.2.2. Secondary Endpoints

The secondary endpoints of this study are as follows:

- Average change of GI severity scores from Day 0 to Day 10 as measured by total change of GSRS scores from Day 0 over the first 10 days (Day 1 to Day 10) divided by total number of days with GSRS recorded
- Average change of GI severity scores from Day 0 to Week 10 as measured by total changes of GSRS score from Day 0 over the first 10 weeks (Day 1 to Week 10) divided by total number of days with GSRS recorded
- Time to first worsening of GSRS in GI severity
- Time to recovery to Day 0 GSRS score from the last occurrence of the worst score in GI severity
- Average change of GSRS score from Day 0 score to Weeks 1, 2, 3, 4, 5, 6, and 8
- Average change of GSRS score from Day 0 to 72 hours from the initiation of randomized study treatment
- Proportion of subjects who require GI symptomatic therapy during the study
- Percentage of subjects who discontinue DMF therapy due to GI-related events from Day 0 to Week 10
- Proportion of subjects who experience flushing events

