The dose of DMF used will be as described in the USPI. Subjects will take DMF for up to 14 weeks, including 8 weeks with the concomitant randomized study treatment (Montelukast or placebo), and will record pertinent information regarding GI-related events in an eDiary.

Information on AEs and SAEs will be collected for possible correlation with GI-related events. For the purposes of this study, relapses of MS will not be considered AEs, and data related to relapses will be captured only if the event is deemed an SAE or results in a subject's discontinuation. Relapses of MS resulting in hospitalization are considered SAEs and will be reported to the FDA. However, they will not be reported as SAEs in the study unless the relapse is complicated by other SAEs or is fatal.

[figure not shown]

Figure 1: Study Design

Abbreviations: BID = twice daily; DMF = dimethyl fumarate; GI = gastrointestinal; QD = once daily. *Use of symptomatic therapies, as specified in Protocol Section 10.3.2, is permitted from Day 10 onward.

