Average change of GSRS score from baseline (Day 0) to Week 1, 2, 3, 4, 5, 6 and 8 will be summarized; a repeated measures model for the change of the GSRS score from baseline, adjusted for age, weight and baseline GSRS score, will be used to estimate effect at each time point. Sensitivity analyses using ANCOVA model for the average change may be performed.

Average change of GSRS score from Day 0 to 72 hours from the initiation of randomized study treatment

Average change of GSRS score from baseline (Day 0) to 72 hours (Day 3) from the initiation of randomized study treatment will be summarized and analyzed by the repeated measures method. No sensitivity analysis will be performed.

Proportion of subjects who take GI symptomatic therapy during the study

From Day 10 onward, subjects are allowed to use symptomatic therapy to treat DMFrelated GI events. The proportion of subjects who take GI symptomatic therapy from Day 10 to Week 10 will be summarized by treatment and analyzed using the Chi-squared test.

[figure not shown]
Percentage of subjects who discontinue DMF therapy due to the GI-related adverse events from Day 0 to Week 10

The proportion of subjects who discontinue DMF due to the GI-related adverse events from Day 0 to Week 10 will be summarized by treatment and analyzed using the Chi-squared test.

Proportion of subjects who experience flushing events

The proportion of subjects who experience flushing events from Day 0 to Week 10 will be summarized for the modified ITT population by treatment group and analyzed using the Chi-squared test. Flushing event as defined as an event coded to any of the following preferred terms: Flushing, Hot flush (under SOC of Vascular disorders), Erythema, Generalized erythema, Skin burning sensation (under SOC of Skin and subcutaneous tissue disorders), Burning sensation (under SOC of Nervous system disorders), Feeling hot (under SOC of General disorders and Administration site conditions), Hyperaemia (under SOC of Vascular disorders).

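### Rescue GI therapy is allowed from Day 10 in four places and only from Day 11 in two; the Day 10 rule opens the last of the ten primary days (effect probably small)

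*Combined protocol and SAP*

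**What the plan says.** Four places set the start at Day 10:

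- Protocol 10.3.2: "From Day 10 onward, but not before, subjects may use the following medications".
- Protocol 4.1, Figure 1 footnote: "Use of symptomatic therapies, as specified in Section 10.3.2, is permitted from Day 10 onward".
- SAP 3.1, Figure 1 footnote: "Use of symptomatic therapies, as specified in Protocol Section 10.3.2, is permitted from Day 10 onward".
- SAP 7.3.4: "From Day 10 onward, subjects are allowed to use symptomatic therapy".

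Two places set it at Day 11. The synopsis (exclusion 8) says "From Screening up to Day 10, use of such therapies is not permitted", and Protocol 8.2 (exclusion 4) repeats the bar and adds "From Day 11 (inclusive), subjects are permitted to take these therapies". The synopsis carries that second sentence too.

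On the averaging window, Protocol 6.2.2 takes the change in GSRS score "over the first 10 days (Day 1 to Day 10) divided by total number of days with GSRS recorded". SAP 7.3.3 uses the same average for the primary endpoint and treats a positive value as worsening.

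On the origin of the day count, Protocol 6.2.1 puts Day 0 on the day before the first randomized dose. SAP 2.1 instead puts it on the first-dose day for subjects who start on the day they reach the threshold. SAP 2.1 places Day 10 ten days after Day 0.

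**The concern.** The two rules cannot both be followed on Day 10. A subject who takes loperamide that day complies with 10.3.2 and breaches 8.2, so sites can handle the same use differently.

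Day 10 is also the last day of the primary window. A score recorded under rescue can pull the average down and, for a subject near zero, change the classification from worsened to not worsened. SAP 7.3.3 has no rule for such scores. Displays by day, such as the Day 10 point on the trajectory plots, would take the whole fall rather than a tenth of it.

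**Working it through.** The documents give no figure for the effect of Day 10 therapy, so there is none to reproduce. The sample size of 118 does not use the rule.

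**Step 1: averaged days open to rescue.** Let F be the date of the first randomized dose. Under SAP 2.1, Day 10 is F+10 for same-day starters (Day 0 = F) and F+9 for next-day starters (Day 0 = F−1). For delayed starters Day 0 is no later than F−1, so Day 10 is no later than F+9.

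| Day count used for the rule | Starter | Day 10 rule: first date | Averaged days open | Day 11 rule: first date | Averaged days open |
|---|---|---|---|---|---|
| SAP 2.1 Day 0 | same-day | F+10 | 1 | F+11 | 0 |
| SAP 2.1 Day 0 | next-day | F+9 | 1 | F+10 | 0 |
| Protocol 6.2.1 Day 0 (F−1) | same-day | F+9 | 2 | F+10 | 1 |
| Protocol 6.2.1 Day 0 (F−1) | next-day | F+9 | 1 | F+10 | 0 |

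On the SAP's count, the Day 10 rule opens 1 of 10 days and the Day 11 rule opens none. On the protocol's count, the Day 11 wording still leaves one day open for same-day starters. The correction therefore has to name the origin of the count as well as the day.

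**Step 2: effect on one subject's average.** With ten recorded days, a fall of d in the overall score on Day 10 lowers the average by d/10. The overall score is the mean of 15 items (SAP 7.3.2). The values of d below are assumptions.

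- One item scored 2, fully relieved: d = 2/15 = 0.133; shift 0.133/10 = 0.013.
- One item scored 3, fully relieved: d = 3/15 = 0.20; shift 0.20/10 = 0.02 (0.20/8 = 0.025 with eight recorded days).
- Larger falls: d = 0.25, 0.5 and 1.0 give shifts of 0.025, 0.05 and 0.10.

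With ten recorded days, status changes only if the average without rescue is above 0 and no greater than d/10. One item point is worth 1/(15 × 10) = 0.0067, so full relief of one item scored 3 matters only when the net change over the ten days is +1 to +3 item points. This example is not an upper bound, because items run to 6 and several can improve together.

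**Step 3: effect on the worsening rate, on assumed inputs.** A simulation took 60% worsening without rescue, between- and within-subject SDs of 0.3 to 0.5, 15% to 30% of subjects rescued on Day 10, and falls of 0.25 to 1.0. If rescue is unrelated to severity, the worsening rate drops by about 0.3 to 3.7 percentage points. If the worst subjects take it, the drop is about 0, because their averages stay positive.

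**The case against.** The strongest reply is that this is a one-day wording slip. Day 10 carries a tenth of the average, and those most likely to need rescue are probably far enough above zero to count as worsened anyway. SAP 5 closes enrolment at about 60 dosed subjects, so an amendment may reach few people before their Day 10. The repeated-measures analysis in SAP 7.3.4 also lets Day 10 be inspected on its own. All of this stands as an argument about size. It does not reconcile the two rules, and the repeated-measures model does not correct the binary endpoint.

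A reader might infer three stronger points that the documents do not support.

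- *The primary result is materially biased.* The number of Day 10 users and the size of their relief are not stated, and the assumed scenarios give small shifts.
- *The whole endpoint hangs on Day 10.* Protocol 16.4.3 could be read as a single-day change, but SAP 7.3.3 defines the average.
- *Day 10 use forces withdrawal.* Protocol 12 requires withdrawal for prohibited medication and cites 10.3.1, which exempts the therapies allowed in 10.3.2. Its other reference, to Section 1, is unclear. Other sections use that reference for the exclusion criteria, but this is too weak to establish that withdrawal is mandatory.

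**Conclusion.** The inconsistency is certain: four places say Day 10 and two say Day 11, with no reading that fits both. Following 10.3.2 on the SAP's day count opens 1 of the 10 primary days to rescue. It becomes 2 for same-day starters if a site counts from the protocol's Day 0. A lower figure of 0 for next-day starters would need sites to count rescue days from the first dose. Footnote b to the Schedule of Events uses that origin for visit dates only, so I do not rely on it.

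The expected effect on the primary result is small but cannot be fixed from the documents. It depends on how many subjects use therapy on Day 10 and how far it lowers their scores. The point warrants correction because it concerns an operating rule inside the primary window and the wording change is simple. It does not call the design or the sample size into question.

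**What to change.** 1. Change Day 10 to Day 11 in Protocol 10.3.2, both Figure 1 footnotes and the permission sentence of SAP 7.3.4, to match the synopsis and Protocol 8.2.
2. State in all six places that days are counted from the SAP 2.1 Day 0, and spell that definition out, because Protocol 6.2.1 differs for same-day starters. No permitted use then falls in Day 1 to Day 10.
3. If sites need a calendar date, F+11 clears the window for every type of starter, but it must appear in all six places. On the protocol's count F+11 is Day 12, so using it in 10.3.2 alone would recreate the conflict with 8.2. It also delays relief by one day for next-day starters, whose SAP Day 11 is F+10.
4. Leave the therapy endpoint window in SAP 7.3.4 as Day 10 to Week 10, so that Day 10 use already permitted is still counted. This suits the protocol's endpoint, "Proportion of subjects who require GI symptomatic therapy during the study". Do not relabel that use as a deviation.
5. Optionally, for subjects already past Day 10, add one sensitivity analysis to SAP 7.3.3 that counts anyone with symptomatic therapy in the eDiary during Day 1 to Day 10 as worsened. Do not substitute the last score before therapy: if a Day 10 flare prompted the rescue, the Day 9 score may be lower than the recorded one, and the substitution would then lower the average.

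The cost is a short protocol amendment, which Protocol 19.3 requires to go to the IRBs, across about 50 sites, plus small SAP edits. It may reach few subjects in time. The optional analysis needs no new data, because SAP 7.2.8 says GI medication is already captured in the eDiary.
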